STATISTICAL ANALYSIS PLAN

STUDY TITLE:

A DOUBLE BLIND, RANDOMIZED, PLACEBO CONTROLLED

STUDY TO EVALUATE EFFICACY AND SAFETY OF

“VIRACIDE”

IN THE MANAGEMENT OF

CORONA VIRUS DISEASE 2019 (COVID-19)

Version No. – 01

Dated: 04th June 2020

Protocol ID – NS-VC-CT01-20

Clinicaltrial.gov ID: NCT04596085

Confidential & Proprietary

the unauthorized use, disclosure, distribution or copying of these information is strictly prohibited

Confidential

Page

1 of 11

Table of Contents

[1 Definitions](#)

[2 Objectives](#)

[3 Analysis Sets](#)

[4 Data handling](#)

[5 Statistical methods](#)

[5.1 Descriptive methods](#)

[5.2 Primary analysis](#)

[5.3 Analysis of the secondary endpoints](#)

[5.4 Safety and/or further analyses](#)

[6 Listings, tables, figures](#)

[7 Graphs](#)

[8 Software](#)

Confidential & Proprietary

the unauthorized use, disclosure, distribution or copying of these information is strictly prohibited

Confidential

Page

2 of 11

1 Definitions

The following abbreviations will be used in this statistical analysis plan.

ITT	Intention-to-treat
PP	Per protocol
IP	Investigational product
AE	Adverse Event
SAE	Serious adverse event
TTCI	Time to clinical Improvement
SPO2	Oxygen saturation
ICU	Incentive Care Unit

Confidential & Proprietary

the unauthorized use, disclosure, distribution or copying of these information is strictly prohibitea

2 Objectives

Primary Efficacy Endpoint:

1. TICI using NEWS Score [Time Frame: First treatment date up to when PCR is negative]

The median time in days from the start of treatment with the study drug / placebo to the persistent achievement of all of the following criteria:

- Stopping a fever (which is defined as a decrease in axillary temperature below 37 ° C without the use of antipyretic drugs);
- Respiratory rate <22 / min;
- Oxygen saturation (SPO2) > 95% when breathing in atmospheric air. Measured using pulse oximetry
- Systolic blood pressure ≤200 mmHg
- Pulse rate 51-90 beats/minute
- Is conscious and alert

[Note: Persistent achievement means the preservation of each of the criteria for at least 7 days.]

2. TTIC using 7-point ordinal scale
3. Rate of progression to severe/critical COVID-19 disease based on NEWS score [Time frame: First treatment date up to 28 days]
4. Rate of progression to severe/critical COVID-19 disease based on 7-point ordinal scale [Time frame: First treatment date up to 28 days]
5. Time to COVID-19 nucleic acid testing negativity in oropharyngeal/nasal swab) [Time Frame: First treatment date up to 28 days]

Confidential & Proprietary

The unauthorized use, disclosure, distribution or copying of these information is strictly prohibited

Secondary Efficacy Endpoints:

1. Incidence of ICU admissions [Time Frame: 28 days]
2. Subject survival rate [Time Frame: 28 days]
3. Incidence of mechanical ventilation [Time Frame: First treatment date up to 28 days]
4. Time to COVID-19 nucleic acid testing negativity in oropharyngeal/nasal swab) [Time Frame: Days 1, 7, 15]
5. Change in clinical or laboratory assessment of comorbid condition [Time Frame: First treatment date up to 28 days]
6. Percent of participants with worsening comorbid condition [Time Frame: First treatment date up to 28 days]

Safety Endpoints

1. Proportion of subjects in the treatment arm who had AE, SAE
2. Proportion of subjects in the placebo arm who had AE, SAE

Confidential & Proprietary

Any unauthorized use, disclosure, distribution or copying of these information is strictly prohibited

3 Analysis sets

Per protocol subset (PP)

Subjects without any Major protocol violation would be included in the per-protocol population, including those subjects who have completed all the visits, who did not take any prohibited medications during the study period and whose CRF was completed as requested.

Modified Intention to treat subset (mITT)

The term “mITT” includes all randomized subjects who met all inclusion/exclusion criteria, administered at least one dose of assigned product with at least completed one visit will be included in the mITT population.

Safety analysis subset

The safety population will consist of all subjects enrolled in the study, who have received at least one dose of study products i.e. mITT population.

Methods of Analysis

Primary Efficacy and secondary endpoints will be analyzed using the PP & mITT population. And Safety variables as per mITT only.

4 Data Handling

Data entry into CRF must be performed as per general CRF data entry guidelines, summarized at the time of data entry feasibility training. Data entry will be made as per source document without interpretation or modification to maintain consistency and accuracy of the data. Study specific

Confidential & Proprietary

Any unauthorized use, disclosure, distribution or copying of these information is strictly prohibited

data entry in CRF will be performed by the assigned study coordinator. Apart from visit specific data, which would primarily be captured in paper, SD, IP diary & Lab reports will also be captured in

CRF directly from the original source or from patients file.

Investigators will maintain the Site Master File, Source Documents, and the Participant Files according to the ICH-GCP guidelines at the site.

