Primary Endpoints	
1. TICI using NEWS Score [Time Frame: First treatment date up to discharge day (PI's discretion as per patients health condition)]
 
The median time in days from the start of treatment with the study drug / placebo to the persistent achievement of all of the following criteria:
 
 • Stopping a fever (which is defined as a decrease in axillary temperature below 37 ° C without the use of anti pyretic drugs); • Respiratory rate <22 /min; • Oxygen saturation (SPO2) > 95% when breathing in atmospheric air. Measured using pulse oximetry • Systolic blood pressure ≤200mmHg • Pulse rate 51-90beats/minute • Is conscious and alert 
[Note: Persistent achievement means the preservation of each of the criteria for at least 7days.]
 
2. TTIC using 7-point ordinal scale
 
3. Rate of progression to severe/critical COVID-19 disease based on NEWS score [Time frame: First treatment date up to 15days]
 
4. Rate of progression to severe/critical COVID-19 disease based on 7-point ordinal scale [Time frame: First treatment date up to 28days]
 
5. Time to COVID-19 nucleic acid testing negativity in oropharyngeal/nasal swab) [Time Frame: First treatment date up to 28days]

Secondary Endpoints	
 1. Incidence of ICU admissions [Time Frame: 28days] 2. Subject survival rate [Time Frame: 28days] 3. Incidence of mechanical ventilation due to COVID-19 infection [Time Frame: First treatment date up to 28days] 4. Change in clinical or laboratory assessment of comorbid condition [Time Frame: First treatment date up to 28days] 5. Percent of participants with worsening comorbid condition [Time Frame: First treatment date up to 28days] 6. Proportion of subjects in the treatment arm who had AE, SAE 7. Proportion of subjects in the placebo arm who had AE, SAE
Subject Selection Criteria	
Inclusion criteria
 
 1. 50 years or older

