Visits of Assessment	
Screening and 3 visits and one telephonic follow-up
 
Screening Inclusion/Exclusion Criteria, Subject Inform Consent, Demography, Medical History, Physical Examination, Vital Signs, HIV; HBsAg; HCV; Hs-CRP; Pulse oximetry; NEWS scoring; 7- point ordinal scoring; Medication list review (medications being taken for comorbid conditions), Lab assessment; Urine analysis Note: Patients who do not meet the study inclusion exclusion criteria during screening should not be randomized into the study.
 
Day 1 Randomization, Vital Signs, Pulse oximetry, AE/SAE, Concomitant Medication, ViraCide/ Placebo treatment start, NEWS scoring; 7-point ordinal scoring
 
Day 7 Physical Examination, Vital Signs, AE/SAE, Concomitant Medication, ViraCide/ Placebo Compliance check, Pulse oximetry; NEWS scoring; 7-point ordinal scoring. (Note: If the subject is discharged on this day as per PI's discretion and patient's health condition then assessment scheduled for day 15 will be carried out on discharge day).
 
Day 15 Physical Examination, Vital Signs, AE/SAE, Concomitant Medication, ViraCide/ Placebo treatment end, RT-PCR for

	
Sars- Co-V2, Hs-CRP, Safety Lab Tests, Pulse oximetry; NEWS scoring; 7-point ordinal scoring, ViraCide/ Placebo Compliance check, Lab assessment including urine analysis
 
Day 28 Phone call follow up for time :
 
 • until negative RT-PCR for Sars-Co- V2, COVID-19 related mortality, • development of any COVID-19 symptom, • development of any worsening of comorbid condition; • Development of new AE/SAE; Resolution status of previous AE/SAEs 
Note: If subject is discharged before Day 15 on PI's discretion as per patients health condition, then assessments scheduled for Day 15 will be carried out on the discharge day (as far as possible and those not performed will be noted on appropriate CRF page) and Day 15 visit will be done telephonically.

Laboratory Investigations	
Screening: Recording RT-PCR- Sars-Co-V2 result; Urine pregnancy test; HIV; HBsAg; HCV; Hs-CRP; Hematology* + Biochemistry + Urine analysis*; ECG
 
Day 1: No labs
 
Day 7: No labs
 
Day 15: Oropharyngeal/nasal swab for PCR- Sars-Co-V2; Hematology* + Biochemistry + Urine analysis*; ECG; Serological biomarker: Hs-CRP

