5.1 Descriptive methods

Participant Disposition

Demographic and Baseline Information

Continuous variables that are Age, weight, BMI, and other demographical characteristics will be summarized by overall using summary statistics i.e. the number of observations, mean and standard deviation with 95% CI (among normal distribution) or median with range (if non-normal distribution). Categorical values like gender and clinical Examination will also be summarized using frequencies and percentages.

Confidential & Proprietary

Any unauthorized use, disclosure, distribution or copying of these information is strictly prohibited

The medical history and Physical examination will be presented using frequencies and percentages of subjects for the Safety population. For continuous data student analysis of variance test and for categorical data Chi square test will be estimated to compare the baseline demographical data between groups and changes during the follow up.

5.2 Efficacy Parameters:

Summary of efficacy parameters – the number of observations, mean and standard deviation with 95% CI (among normal distribution) or median with range (if non-normal distribution)

Analysis of Primary Efficacy Parameters

In this study median Time to Clinical Improvement (TTCI) using NEWS Score [Time Frame: First treatment date up to when PCR is negative] TTIC using 7-point ordinal scale [Time Frame: First treatment date up to when PCR is negative] will be assessed for both Test and Placebo group and compare the mean time between two arms by using Mann Whitney U test.

Other variables that are Rate of progression to severe/critical COVID-19 disease based on NEWS score and 7 point ordinal scale [Time frame: First treatment date up to 28 days] will be compared by using Chi Square test.

Other parameter like Time to COVID-19 nucleic acid testing negativity in oropharyngeal/nasal swab) [Time Frame: First treatment date up to 28 days] will be estimated by Student t test or one way analysis of variance. If data is

Confidential & Proprietary

Any unauthorized use, disclosure, distribution or copying of these information is strictly prohibited

not passing normality for continuous variable Mann Whitney test will be assessed instead of student t test.

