5.4 Safety Analysis

Incidence and rate of adverse events.

AEs and SEs will be summaries counting both the number of separate events and the number of subjects experiencing events occurring during the study period will be provided overall, per system organ class and preferred term by presenting.

Confidential & Proprietary

the unauthorized use, disclosure, distribution or copying of these information is strictly prohibitea

Furthermore, similar summaries will be provided stratified according to the seriousness, severity, and relationship to the study medication. The percentage of cases with an event will be analyzed and compared by the Chi-Square test. Mean changes in in vital signs and Laboratory variables, will be assessed by using student t-test for with in groups and analysis of variance for comparison between groups.

6. Listing of Tables

- Participant Disposition
- Demographical and baseline characteristics with comparison of demographical and baseline characteristics
- Profile of Medical History and clinical Examinations
- Changes in Vital Signs
- Comparison of Mean Time to Clinical Improvement (TTCI) using NEWS Score
- Comparison of Mean Time to Clinical Improvement (TTCI) using 7 point ordinal scale.
- Rate of progression to severe/critical COVID-19 disease based on NEWS score [Time frame: First treatment date up to 28 days
- Rate of progression to severe/critical COVID-19 disease based on 7point Ordinal scale [Time frame : First treatment date up to 28 days

Confidential & Proprietary

The unauthorized use, disclosure, distribution or copying of these information is strictly prohibited

- Mean Time to COVID-19 nucleic acid testing negativity in oropharyngeal/nasal swab) [Time Frame: First treatment date up to 28 days]
- Incidence of ICU
- Profile of subject survival rate
- Incidence of Mechanical ventilators
- Time to COVID-19 nucleic acid testing negativity in oropharyngeal/nasal swab) [Time Frame: Days 1, 7, 15]
- Percent of participants with worsening comorbid condition [Time Frame: First treatment date up to 28 days]
- Changes in clinical assessment of co morbid conditions
- Comparison of Changes Laboratory Variables
- Profile of adverse events in each group
- Profile of Serious adverse events in each group

7. Graphs

Individual Graphs for all Primary and secondary variables

8. Software

SPSS Version 10.0

Confidential & Proprietary

The unauthorized use, disclosure, distribution or copying of these information is strictly prohibited

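### Primary endpoint 5 (time to RT-PCR negativity) is analysed as a mean time, but the one scheduled swab only bounds that time and the SAP has no rule for scoring it

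*SAP*

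**What the plan says.** **Endpoint.** The protocol synopsis lists "Time to COVID-19 nucleic acid testing negativity in oropharyngeal/nasal swab) [Time Frame: First treatment date up to 28days" as the fifth primary endpoint. SAP section 2 repeats it: "Time to COVID-19 nucleic acid testing negativity in oropharyngeal/nasal swab) [Time Frame: First treatment date up to 28 days".

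**Analysis.** SAP section 5.2 says that the variable "will be estimated by Student t test or one way analysis of variance". For data "not passing normality for continuous variable Mann Whitney test will be assessed instead of student t test". SAP section 6 plans a table titled "Mean Time to COVID-19 nucleic acid testing negativity in oropharyngeal/nasal swab) [Time Frame: First treatment date up to 28 days".

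**Swab schedule.** The protocol's Laboratory Investigations record the screening RT-PCR result, list no laboratory tests on Days 1 and 7, and then give "Day 15: Oropharyngeal/nasal swab for PCR- Sars-Co-V2". If a subject is discharged sooner, "then assessments scheduled for Day 15 will be carried out on the discharge day (as far as possible", "and Day 15 visit will be done telephonically". Day 28 is a telephone call. It asks about the time until a negative RT-PCR, but no repeat swab is scheduled.

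**Scoring.** SAP section 4 (Data Handling) covers CRF entry only. Nowhere does the SAP say what time is assigned to a subject whose swab is negative, positive or missing. It names no censored-data method.

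**A second version of the endpoint.** SAP secondary endpoint 4 lists the same variable at Days 1, 7 and 15, with an analysis in section 5.3 and a table in section 6. The protocol's secondary endpoints do not include it, and its laboratory schedule has no swab on two of those three days.

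**The concern.** A t test, an analysis of variance and a Mann-Whitney test each need one value per subject. The schedule does not supply a clearance time. It supplies a swab date and a result, so each time is known only to lie before that date (negative) or after it (positive). The planned mean is therefore not estimable, whichever scoring rule is adopted.

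Some rule must still be adopted before software can produce a p-value. Because the SAP has none, the rule for a primary endpoint could be settled after the data are seen. The candidate rules do not agree. One of them, comparing swab dates among negatives, measures mainly when subjects were swabbed and hardly at all when they cleared virus. This affects one of five primary endpoints.

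**Working it through.** **Plan's own figures.** The protocol needs 112 completers (56 per arm) and enrols 124 for 10% dropout: 112 × 1.10 = 123.2, rounded up to 124. That step reproduces. The 112 does not, because no effect size, rate or test is given. The figures below use 56 per arm.

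**Step 1: what one swab can say about the mean.** Suppose that every swab is taken at 15 days, 80% are negative and the rest clear by 28 days.
- Lowest possible mean: 0.80 × 0 + 0.20 × 15 = 3.0 days.
- Highest possible mean: 0.80 × 15 + 0.20 × 28 = 17.6 days.
- Reported mean: 15.0 if positives are dropped or set to 15, and 17.6 if they are set to 28.

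Counting elapsed time from Day 1 shortens the swab times by a day and does not change the point.

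**Step 2: assumptions for an illustration.** The documents give none of these: exponential clearance, control median 10 days, hazard ratio (HR) 1.75 where there is an effect, and swabs at 6 days (early discharge) or 14 days. P(negative by day d) = 1 − 2^(−d × HR/10).
- Control: 0.340 at 6 days, 0.621 at 14 days.
- HR 1.75: 0.517 and 0.817.

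**Step 3: why comparing negatives by swab date hides an effect.** With 30% swabbed early in both arms:
- Control negatives: 0.3 × 0.340 + 0.7 × 0.621 = 0.537. Early share 0.102/0.537 = 0.190. Mean swab day 14 − 8 × 0.190 = 12.5.
- Treated negatives: 0.3 × 0.517 + 0.7 × 0.817 = 0.727. Early share 0.155/0.727 = 0.213. Mean swab day 14 − 8 × 0.213 = 12.3.

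The true means are 10/ln 2 = 14.4 days and 14.4/1.75 = 8.2 days. A true gap of about 6 days becomes about 0.2 days. The proportion negative still differs by 0.727 − 0.537 = 0.19.

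**Step 4: why it can also create an effect.** With no viral difference and 40% v 20% swabbed early:
- Early shares among negatives: 0.136/0.509 = 0.267 and 0.068/0.565 = 0.120.
- Mean swab days: 11.9 and 13.0, a spurious gap of about 1.2 days.
- The pooled proportion is also shifted, 0.509 v 0.565, against the arm swabbed earlier.

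**Step 5: simulated rejection rates** (two-sided 5%, 56 per arm, 2,000 to 20,000 runs per figure). The rank test places non-negatives last, or scores them at Day 28.

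| Scenario | Negatives only, t test | Rank test | Proportion negative, Newcombe 95% CI |
|---|---|---|---|
| HR 1.75, 30% v 30% early | 5% | 50% to 54% | 53% to 56% |
| HR 1.75, all swabs on one day | 0% | as the proportion | 65% |
| No effect, 30% v 30% | 5% | 5% | 5% |
| No effect, 40% v 20% | 31% | 5% | 8% to 9% |
| No effect, 60% v 10% | not shown | 8% | 30% to 32% |
| No viral effect, clearance drives discharge and discharge differs by arm | 55% to 57% | 9% to 10% | 6% |

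The last row covers two settings for P(early swab if cleared by day 6)/P(early swab if not): 0.80/0.19 v 0.40/0.10, and 0.90/0.14 v 0.50/0.045.

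A complementary log-log model on actual swab dates has 58% power at HR 1.75. Its false-positive rate is 5% when timing is unrelated to clearance and 10% to 16% in the two settings of the last row. With 62 per arm and 10% of swabs missing and counted as not negative, the proportion has 52% power.

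**The case against.** **Mann-Whitney is already in the SAP, and with a sensible score it works.** This stands. With non-negatives ranked last it keeps about 5% false positives at 40% v 20% early swabs and has nearly the power of the proportion. A reader might infer that the endpoint must be replaced by a proportion. The figures do not support that: each analysis is the better one in some scenario. What is missing is the rule, and no score turns the result into a mean clearance time.

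**The alarming figures belong to a rule that the SAP does not state.** This also stands. A reader might infer that the plan carries a false-positive rate of 31%, or of 55% and more. It does not follow. The SAP nowhere says that only negatives will be compared. Those figures also need discharge timing to differ by arm without a viral effect. The trial is double blind and discharge is at the investigator's discretion, so a systematic gap is unlikely if the drug has no effect of any kind. With equal timing the rate is 5%. The loss of power needs no such gap.

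**The Day 28 call collects time to a negative test.** Partly. A later test may narrow the interval for a subject who was positive at the swab. None is scheduled, the documents do not say how a reported date would be used, and a later test cannot date clearance that came before a negative swab.

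**The SAP implies swabs on Days 1, 7 and 15.** That conflicts with the protocol's schedule. Such data would still be interval-censored.

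**Conclusion.** The point holds and should be fixed before unblinding. One scheduled swab cannot yield the mean time that SAP sections 5.2 and 6 promise, and the SAP leaves open the rule that decides the result. On the assumptions shown, that choice moves power at HR 1.75 from about 5% (negatives only) to about 50% to 56% (rank test or proportion) with equal swab timing. The absence of a scoring rule and the impossibility of a mean rest on the documents alone. The sizes rest on the assumed clearance distribution, hazard ratio and swab days, and are not estimates for this trial.

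The documents do not support the stronger conclusions that the plan as written has an inflated false-positive rate, or that only one replacement analysis is acceptable. No candidate is unbiased in every scenario, so swab timing must be visible by arm.

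**What to change.** 1. In SAP sections 5.2 and 6, stop reporting a mean time to negativity, and do not analyse swab dates among negatives only.
2. Before unblinding, specify one primary analysis in all mITT subjects. It can be the proportion RT-PCR negative at the scheduled swab (risk difference with 95% CI), or a rank test with subjects not shown negative ranked last. Give the other as a sensitivity analysis, or an interval-censored model using actual swab dates and any dated later tests.
3. State how missing swabs are counted, with a sensitivity analysis, because swabs may be missed through early discharge.
4. Tabulate swab day and missing swabs by arm. State that the pooled proportion is biased if swab timing differs by arm, and that the rank test and the swab-date model are biased if clearance drives discharge and discharge differs by arm.
5. Delete SAP secondary endpoint 4 with its analysis and table, or reconcile it with the protocol's swab schedule.

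**Cost.** The change is to wording and needs no extra swabs. If the proportion is chosen, endpoint 5 must be reworded in the protocol as well as in the SAP. The trial gives up a claim about an observed mean time to clearance, which this schedule could not have supported.

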5.3 Analysis of Secondary Efficacy Parameters

For Secondary efficacy variables that is Incidence of ICU admissions, subjects survival rate , incidence of mechanical ventilation , percentages of participants with worsening co morbid conditions and changes in clinical comorbid conditions will be analyzed using Chi square test variance (Kruskal Wallis test) for between Groups. If observed mean difference is significant Friedman's post hoc test will be applied to assess which group is significant. Average Time to COVID-19 nucleic acid testing negativity in oropharyngeal/nasal swab) will be assessed at each time points and data will be analyzed by using analysis of variance. If data is not normal, analysis of variance with kruskal wallies will be estimated.

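### SAP secondary endpoint 4 repeats primary endpoint 5 at Days 1, 7 and 15, but the only scheduled on-study swab is on Day 15 or at earlier discharge

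*SAP*

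**What the plan says.** Both documents make time to PCR negativity the fifth primary endpoint, followed to Day 28. The Protocol synopsis has "5. Time to COVID-19 nucleic acid testing negativity in oropharyngeal/nasal swab) [Time Frame: First treatment date up to 28days", and SAP Section 2 has "5. Time to COVID-19 nucleic acid testing negativity in oropharyngeal/nasal swab) [Time Frame: First treatment date up to 28 days". SAP Section 2 then lists the same variable as secondary efficacy endpoint 4: "Time to COVID-19 nucleic acid testing negativity in oropharyngeal/nasal swab) [Time Frame: Days 1, 7, 15". The Protocol's list of seven secondary endpoints has no such entry.

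SAP 5.3 says of the secondary version that the average time "will be assessed at each time points and data will be analyzed by using analysis of variance", with Kruskal-Wallis as the non-normal alternative. SAP 5.2 gives the primary version a t test or one-way analysis of variance, with Mann-Whitney as the alternative. SAP Section 6 plans a separate table for each.

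The Protocol's Laboratory Investigations row has, at screening, "Recording RT-PCR- Sars-Co-V2 result". It states that there is no laboratory work on Days 1 and 7, and then gives "Day 15: Oropharyngeal/nasal swab for PCR- Sars-Co-V2". Two notes move that swab. The Day 7 visit entry brings the Day 15 assessments, swab included, forward to Day 7 for subjects who leave then; its note begins "If the subject is discharged on this day as per PI's discretion and patient's health condition then assessment scheduled for day 15 will be carried". For any discharge before Day 15, "then assessments scheduled for Day 15 will be carried out on the discharge day (as far as possible", and the Day 15 visit becomes a telephone contact. The Day 28 call asks about the time until a negative RT-PCR; no Day 28 swab is listed.

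**The concern.** A secondary endpoint tied to three visits implies PCR results at those visits. The Protocol does not plan to collect them, so the SAP specifies an analysis that its data source cannot supply. A programmer reading SAP 5.3 would also not know what to compute at each visit: a mean time, a proportion negative, or something else.

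Two things are at stake. First, a Day 7 table could be produced from whatever swabs happened to be taken that day. It would look like a randomized comparison although discharge decided who was in it. Second, the same swab is reported in two endpoint tiers, with separately stated tests and tables. The SAP has no multiplicity rule or hierarchy to say how the two results relate, so a reader could take the second as independent support for the first.

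**Working it through.** The plan gives no figure for this endpoint to reproduce. The check sets the endpoint's time frame against the Protocol's visit and laboratory schedules.

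**Swabs by time point**

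| Time point | Scheduled study swab | Source in the Protocol |
|---|---|---|
| Screening | None required; an existing result is recorded | Laboratory Investigations, screening |
| Day 1 | 0 | Laboratory Investigations; Day 1 visit list has no RT-PCR |
| Day 7 | 0, or 1 if discharged that day | Laboratory Investigations; note to the Day 7 visit |
| Day 15 | 1, unless discharged earlier | Laboratory Investigations; Day 15 visit list |
| Day 28 | 0 (telephone report) | Day 28 visit entry |

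Each subject therefore has at most one scheduled on-study swab. Write n7, n15 and n_other for the subjects in an arm swabbed on Day 7, on Day 15, and on another discharge day. Among the 56 completed cases planned per arm, n7 + n15 + n_other ≤ 56. Every subject who adds to n7 is lost from n15. The documents give no expected discharge pattern, so the split cannot be estimated.

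**Day 1.** No swab is scheduled. Entry requires a positive RT-PCR and Day 1 is the start of treatment, so a Day 1 comparison would have no data and could not show a treatment effect.

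**Day 7.** The only swabs are those of subjects discharged that day. Discharge is at the investigator's discretion according to the patient's health, and it comes after randomization. The n7 subjects in the two arms are selected on a post-randomization judgement and are not the randomized groups.

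**Day 15.** Subjects swabbed at an earlier discharge have no scheduled Day 15 swab. A strict Day 15 analysis loses them; including them means using the discharge swab.

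**Overlap with primary endpoint 5.** The Day 15 or discharge swab is the only scheduled on-study PCR source for both endpoints. The primary endpoint runs to Day 28 and can also use results reported in the Day 28 call. On the schedule, the secondary endpoint's data are at most a subset of the primary endpoint's data.

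**The quantity.** Time to an event gives one value per subject, not one per visit. With a single swab, a negative result shows only that negativity was reached by the swab day. If the swab day is taken as the time, a subject discharged and negative on Day 7 scores 7 and a subject swabbed and negative on Day 15 scores 15, even if both cleared the virus on the same day. The recorded time would then partly measure when discharge occurred.

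**The tests.** With two arms, one-way analysis of variance is the pooled t test (F = t²). Kruskal-Wallis is the large-sample Mann-Whitney test without continuity correction (H = z²). The secondary endpoint therefore brings no new method. Whether it gives the same p-value depends on the data entering each test, and these can differ.

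**The case against.** The strongest case on the other side is that this is a small inconsistency that is easily overstated. Three stronger readings are tempting, and the documents support none of them.

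- *The two endpoints use the same data.* They need not. A subject still positive at Day 15 can contribute a later, telephone-reported time to the primary endpoint but not to one that ends at Day 15.
- *The secondary p-value must reproduce the primary one.* Equivalent tests give equal p-values only on identical observations. The time frames differ, and the normality rule could send the two analyses down different branches. Nor can an undefined quantity be shown to reproduce a defined one.
- *Two of the three comparisons cannot be produced.* That is true of Day 1 only. Subjects discharged on Day 7 do have the swab moved to that day, so some Day 7 data may exist. The fault there is selection, not absence.

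It is also fair to say that neither document assigns alpha to the secondary endpoints or makes a conclusion depend on endpoint 4, so double presentation is a reporting risk and not a demonstrated error. Deletion is not the only remedy, since redefining the endpoint would also resolve the mismatch. A replacement proportion would draw on the same swab, taken on days that vary with discharge; that limitation has to be shown openly.

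What remains is that the stated visits do not match the schedule, the endpoint is absent from the Protocol's secondary list, and the planned quantity is undefined.

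**Conclusion.** The point holds as a mismatch between the SAP and the Protocol, and the SAP should be corrected. Of the three named time points, Day 1 has no scheduled swab, Day 7 has one only for subjects discharged that day, and Day 15 has one for subjects not discharged earlier. The analysis in SAP 5.3 cannot be carried out as stated. Apart from any discharge-selected Day 7 table, the endpoint reduces to the single swab that already feeds primary endpoint 5.

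The sample size of 124, the 80% power and the 5% significance level are unaffected.

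The conclusion assumes that the Protocol's laboratory and visit schedules govern when swabs are taken. Unscheduled PCR tests done in routine care could add results, but neither document says that they will be collected at Days 1 or 7. One swab plus a telephone report is also a thin basis for the time measured by primary endpoint 5; that is a wider question than this correction.

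**What to change.** Either of two SAP edits resolves the point.

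1. Delete secondary efficacy endpoint 4 from Section 2, its sentence from 5.3, and its table (Days 1, 7, 15) from Section 6.
2. Replace it in those three places with the proportion PCR-negative at the Day 15 or discharge swab, by arm, with the difference between arms and its 95% confidence interval. State that each subject contributes one swab. Tabulate the day of swab by arm, because discharge timing varies. Give the number without a swab by arm, because the Protocol allows discharge-day assessments to be missed. Label the result as supportive of primary endpoint 5, not as independent evidence.

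Under the second option, the secondary lists in the Protocol and SAP should be brought into agreement. The cost is an SAP revision and at most one replacement table. Neither option needs new data or a change to the visit schedule or sample size.
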